Protocol Title: Short vs Long Dental Implants for the Fixed Rehabilitation of the Fully Edentulous Mandible

CEAOUSUN1327012010

PI: [name], DDS

Version Date: 20/06/2019

NCT03509402

Background, Significance, and Rationale

The clinical use of dental implants in the rehabilitation of totally and partially edentulous patients represents to date a long-term well documented and highly predictable procedure (for review see Cochran 1996, Esposito et al. 1998a, b). Historically, surgeons aimed for placement of the longest possible implants, in order to reach high bone-to-implant contact rates with the machined implants available at that time. The use of modern "rough" implants has been demonstrated to positively correlate with bone-to-implant contact rate and bone anchorage, leading to a significant enlargement of clinical indications for implant-supported rehabilitations (Gotfredsen et al. 1992; Cooper et al. 2000; Ivanoff et al. 2001; Shalabi et al. 2006).

The available amount of bone still remains the main limitation for implant placement. In cases of reduced bone height, standard length fixtures could be inserted only after advanced surgical treatments, such as vertical ridge augmentation, mandibular nerve transposition, and maxillary sinus lift. Patients often refuse such invasive procedures, ending up renouncing implant rehabilitation. For this reason, the possibility of using short implants is particularly fascinating, since it provides reliable solutions also in the numerous cases of reduced bone height, significantly expanding clinical indications for implant treatment. The use of short implants, moreover, presents also "absolute" benefits for patients in terms of limited foreign body, less invasive surgery (less biological tissue replacement), and reduced risk of damaging anatomical structures.

For "short" implants we refer to fixtures with an intraosseous length $\leq 8 \text{ mm}$ (Renouard & Nisand 2006).

Short implants historically have been associated with higher failure rates than longer ones. On the other hand, a number of studies have failed to find differences in the survival rate of short and long implants (for review see Renouard & Nisand 2006, Morand & Irinakis 2007).

The discrepancies between these two groups of studies may relate to different factors such as the implant surface employed, the surgical protocol adopted in relation to the local bone density, the type of edentulism, and the prosthetic technique chosen.

Well-designed randomized controlled clinical trials demonstrating the efficacy of short implant rehabilitations are lacking to date.

The clinical performance of short and long implants should be compared at the level of areas having a good and comparable bone quality, the same bone height (this assumes the installation of short implants in sites able to receive longer ones), and for the resolution of the same type of edentulism by means of an identical prosthetic solution.

A reliable option is represented by 5 implants positioned in the interforaminal region of edentulous mandibles having bone height sufficient to receive standard-length implants, supporting a fixed full-arch prosthesis. The anterior mandibular region is usually characterized by high bone quality. Furthermore, the above-mentioned type of full-arch implant-supported rehabilitation possesses the best evidence of long-term success (Ekelund et al. 2003; Bryant et al 2007), being historically the first one performed and, to date, the most predictable too.

Specific Aims and Hypotheses

The aim of the present study is to evaluate the efficacy of 6 mm short implants compared with 11 mm long implants in comparable anatomic, surgical (no need for bone augmentation procedures), and prosthetic (fixed full-arch mandibular prosthesis) conditions. In particular, the null hypothesis is that there is no difference in terms of marginal bone level change (MBLc) between short and longer implants from prosthetic installation to 5 years of follow-up.

Study design and general information

This study has been designed as a multicenter parallel-group randomized controlled clinical trial (RCT) with a 1:1 allocation ratio. Three italian centers will be involved to the study. It will be reported according to the

CONSORT statement (http://www.consort-statement.org/). The Declaration of Helsinki principles will be followed, and all patients will sign a written informed consent form. The research protocol has been approved by the ethical committee of the University of Campania "Luigi Vanvitelli" (Aut. N. 13/2010).

Primary and secondary outcomes

The primary outcome will be the radiographic MBLc expressed as the change of MBL from prosthetic installation to the follow-up.

The secondary outcomes will include: (i) implant survival rate, (ii) prosthesis survival rate, (iii) biological or technical complications. Surviving implant or prosthesis will be considered those still in function at the follow-up. Biological complications included peri-implant mucositis, defined as a reversible inflammation of the soft tissues surrounding an implant in function with no loss of supporting bone, and peri-implantitis, defined as an inflammatory process affecting the tissues around an osseointegrated implant in function resulting in loss of supporting bone (Zitzmann & Berglundh 2008. Technical complications will be categorized in minor and major complications. The formers require only chair side repair and included screw loosening, and veneer material fracture. The latter require additional laboratory procedures and/or replacement components and included prosthesis or framework fracture, screw fracture, implant fracture, extended wear requiring veneer renewal.

Sample size calculation

Sample size calculation revealed that group sample sizes of 13 per group achieved 80% power to detect noninferiority using a two-sample, one-sided test. The margin of non-inferiority (δ), that is the threshold value judged as clinically relevant, was 1.0 mm. The true difference between the means was assumed to be 0.0. In consideration of the one-tail nature of the non-inferiority test, the significance level (alpha) was set at 0.025. The data were drawn from populations with standard deviations of 0.9 and 0.9. Such a value was based on the long-term marginal bone loss data from the population of mandibular edentulous patients rehabilitated with Toronto bridges supported by conventionally loaded inter-foraminal long implants (Ekelund, Lindquist, Carlsson, & Jemt, 2003). Fifteen patients per group will be recruited to compensate for possible drop-outs.

Patient enrollment

Inclusion criteria will be age between 18 and 75 years, total mandibular edentulism for at least 8 months, sufficient amount of native bone (no previous bone augmentation procedures) in the inter-foraminal area to host 11 mm-long and 4 mm-wide implants with \geq 1 mm of bone at the buccal and lingual aspects and \geq 3 mm of inter-implant distance (determined by computed tomography), systemic health and compliance with good oral hygiene. Exclusion criteria will be any disease, medication or drug that could jeopardize healing, osseointegration or treatment outcome, severe bruxism or other parafunctional habits, and unrealistic aesthetic demands. Smoking habit will be registered as heavy smoker (\geq 10 sig./day), light smoker (<10 sig./day), nonsmoker or former smoker. Patient eligibility in terms of bone dimensions will be determined on computer tomography (CT) scans, with the aid of an implant planning software.

Preparing and planning phase

Eligible patients received a complete anamnestic and clinical examination; hopeless teeth will be extracted and remaining teeth will be periodontally and restoratively treated, if needed. A 15% cut-off for full-mouth plaque score and full-mouth bleeding score will be requested for dentate patients. The prosthetic project will be accurately planned on cast models mounted in an articulator. When possible, the previous denture will be used as a reference.

Randomization and allocation concealment

The randomization and the allocation concealment will be carried out using a computer-generated randomization list and sealed sequentially numbered opaque envelopes by a person not otherwise involved in the study. Envelopes will be consecutively opened at the leading center and communicated to the surgeon at the first surgery.

First surgical phase

Implant positioning will be performed by expert clinicians, following the same shared surgical protocol. A computer-aided bone-supported pilot surgical guide will be used during implant placement. All patients will be treated under local anesthesia using mepivacaine or articaine with adrenaline 1:100,000. A full-arch crestal incision, with distal releasing incisions if needed, will be performed and full thickness flaps will be raised. The mental nerves will be visualized and isolated. Five parallel implant sites will be prepared by calibrated burs and five 4 mm-wide implants (OsseoSpeed TX, Astra Tech Implant System, Dentsply Sirona Implants, Mölndal, Sweden) will be installed anterior to the mental foramens following the outline described by the manufacturer. 6 mm-long implants and 11 mm-long implants in the test and control groups will be placed, respectively. A minimum of 3 mm of inter-implant distance and 1 mm of bone at the buccal and lingual aspects will be required, with no need for augmentation procedures (if augmentation will be required, the patient would have been excluded from the study). If needed, an osteoplasty of the alveolar ridge will be placed flash to the bone. At the end of the surgical procedure cover screws will be positioned and a careful adaption of the flaps by means of an accurate suture will be assured in order to obtain primary closure and full periosteal coverage.

Postoperative care

The patients will be instructed to rinse with a chlorhexidine 0.12% mouthwash twice a day for 2 weeks and to avoid using the denture. Liquid and semisolid food will be prescribed for the first postoperative week, after which the sutures will be removed. Two weeks after the surgery, the denture will be properly relined avoiding direct contact with the fixture until the second-stage surgery. Patients will be controlled at 4, 8, and 12 weeks.

Second surgical phase and prosthetic procedures

After 3 months of healing all implants will be exposed by separated linear incisions, cover screws will be removed and replaced by healing abutments. After 1 week, the final abutment (Uni-abutment, Astra Tech Implant System, Dentsply Sirona Implants, Mölndal, Sweden) will be screwed on each implant and an abutment-level impression will be registered. Expert clinicians will follow all the prosthetic phases. All patients will receive a fixed screw-retained full-arch prosthesis with distal cantilevers. The length of the bridge cantilevers will be calculated to minimize implant overloading (Mericske-Stern, Taylor & Belser, 2000). All prosthetic procedures will be made according to the Astra Tech Implant System procedures and products manuals.

Supportive peri-implant therapy

Patients will be instructed in proper hygiene measures, suitably designed and based on their individual needs, including tooth brushing, interdental brushing, flossing, and rinsing with an antiseptic mouth. Patients will be recalled every six months for a control visit and professional supragingival ultrasonic debridement and polishing.

Baseline and follow-up examinations

Radiographs and clinical examinations will be performed, together with primary and secondary outcome assessment, at baseline (final restoration placement), and after 1, 3 and 5 years of loading.

Clinical examination will include visual inspection to detect signs of inflammation as well as the occurrence of technical complications. Peri-implant probing depth, the presence of visible plaque and bleeding/suppuration on probing around implants will be also evaluated.

Peri-apical radiographs will be taken with Rinn Universal Collimator (Dentsply RINN, York, PA, USA) to limit exposure levels and Rinn film holders (XPC Extension Cone Paralleling System, Dentsply RINN, York, PA, USA), for correct positioning. Film-holder's position will be noted down for each implant site to increase reproducibility. The MBL will be determined (ImageJ 1.48a, National Institutes of Health, Bethesda, MD, USA) as the distance between the top of the micro-thread implant region and the most coronal level of the boneto-implant contact, using inter-thread distance for calibration. All the radiographic measurements will be performed by an experienced examiner not otherwise involved in the study, who will be kept unaware of the implant length by duly masking the radiograms. Mesial and distal MBL will be measured at each fixture and the MBLc from the baseline will be calculated at each follow-up (negative values in case of bone loss). Mean values will be calculated at the implant, patient and group level.

Statistical analysis plan

Descriptive statistics (means, standard deviations) of continuous variables and relative frequencies of discrete variables will be computed for each group separately using a statistical software program. Data will be analysed by an examiner blinded to the experimental groups using the patient as the statistical unit unless differently specified. Intention-to-treat (ITT) analysis will be adopted. The Fisher exact test for discrete intergroup variables and the one-sided Mann-Whitney U-test for MBLc values will be applied, because of the nature of the data. For primary outcome, statistical significance will be set at the alpha level of 0.025 using a one-sided test, while for two-sided tests statistical significance will be set at the alpha level of 0.05.

References

Bryant SR, MacDonald-Jankowski D & Kim K. (2007) Does the type of implant prosthesis affect outcomes for the completely edentulous arch? International Journal of Oral and Maxillofacial Implants 22 Suppl, 117-39.

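### Surgical and healing-phase harms are not prespecified in either arm: the named complications concern implants in function or prosthetic failures, and outcome assessment starts only at final restoration

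*Combined protocol and SAP*

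**What the plan says.** **Outcomes.** The section on primary and secondary outcomes lists the secondary outcomes as "i) implant survival rate, (ii) prosthesis survival rate, (iii) biological or technical complications". It then describes the third:

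- Biological: "Biological complications included peri-implant mucositis, defined as a reversible inflammation of the soft tissues surrounding an implant in function", and "peri-implantitis, defined as an inflammatory process affecting the tissues around an osseointegrated implant in function".
- Technical, minor: "The formers require only chair side repair and included screw loosening, and veneer material fracture".
- Technical, major: these "included prosthesis or framework fracture, screw fracture, implant fracture, extended wear requiring veneer renewal".

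**Surgery and healing.** Under First surgical phase, both arms follow one shared protocol: a full-arch incision, full-thickness flaps and five implant sites. In addition, "The mental nerves will be visualized and isolated". Under Postoperative care, sutures come out after the first week and "Patients will be controlled at 4, 8, and 12 weeks"; nothing is said about what is assessed or written down at those visits. A second surgery follows at three months.

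**Assessment.** Baseline and follow-up examinations places the first outcome assessment at the final restoration, then at 1, 3 and 5 years of loading. The clinical examination covers inflammation, technical complications, probing depth, plaque, and bleeding or suppuration on probing.

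**Rationale.** The background section counts among the benefits of short implants "less invasive surgery (less biological tissue replacement), and reduced risk of damaging anatomical structures".

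**The concern.** The operation is the part of this trial with the most obvious potential for harm, and it falls outside everything the plan defines as a complication. A patient who wakes with a numb lip, or whose wound opens in the second week, has no event under the wording of outcome (iii). Nothing in the examination schedule is designed to pick such an event up later.

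What is at stake is what the trial can say about safety. A report could show a reassuring complication table in both arms that is silent on surgical harm. Unlike an analysis choice, this cannot be repaired at the end: data that were not collected in a standard way cannot be filled in. The background also puts forward lower surgical risk as a benefit of short implants, and readers will look for at least descriptive data on it.

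**Working it through.** **1. The provisions side by side**

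| Period | What happens to the patient | What the plan defines or measures |
|---|---|---|
| First surgery | Flaps, five implant sites, nerve isolation | No outcome named |
| Suture removal; 4, 8 and 12 weeks | Healing, visits held | No assessment stated |
| Second surgery, at 3 months | Implants exposed, healing abutments placed | No outcome named |
| Final restoration | Prosthesis placed | First outcome assessment |
| 1, 3 and 5 years | Loading | Mucositis, peri-implantitis, mechanical events, survival |

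Two independent features lead to the same gap. By definition, both biological conditions need an implant in function. By timing, outcome assessment starts more than three months after first surgery. The examination list has no sensory or wound check, and the statistical analysis plan section has no harms analysis beyond the general Fisher test for discrete variables.

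**2. The plan's own figure**

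Inputs from Sample size calculation: margin 1.0 mm, SD 0.9, true difference 0, one-sided alpha 0.025, power 80%.

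n per group = 2 × SD² × (z₀.₉₇₅ + z₀.₈₀)² / margin² = 2 × 0.81 × (1.960 + 0.842)² / 1.0² ≈ 12.7, rounded up to 13.

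The stated 13 reproduces (normal-approximation power at 13: 80.9%), with 15 recruited. It concerns marginal bone level change only. Adding a descriptive harms outcome does not alter it.

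**3. What 15 per arm can say about harms**

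- *No events seen.* Exact two-sided 95% upper limit for 0/15: 1 − 0.025^(1/15) = 21.8%. With 13 patients evaluable: 1 − 0.025^(1/13) = 24.7%.
- *Smallest split against zero with p<0.05, two-sided Fisher test.* For 5/15 against 0/15, p = 2 × C(15,5)/C(30,5) = 2 × 3003/142506 = 0.042. For 4/15 against 0/15, p = 2 × 1365/27405 = 0.10.
- *Power of that test.* The documents give no event rates, so these are assumptions: 5% against 20% gives 8%; 5% against 30% gives 27%; 5% against 50% gives 74%.
- *Chance that at least one of the 30 patients has an event*, 1 − (1 − p)^30, again for assumed rates common to both arms: 26% at p = 1%, 79% at 5%, 96% at 10%.

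So a formal comparison is out of reach for any modest difference. Yet unless such harms are rare, there would probably be something to record.

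**The case against.** **The list is not stated to be closed.** A reader might infer that an early harm could never be counted. The text does not say that: it uses wording of inclusion, with no statement that other events are barred. This stands. The gap does not depend on closure, because definitions, timing and examination content all point the same way. Nor does the lack of a prespecified outcome prove that a nerve injury would go unreported. Patients are seen during healing and recalled every six months, and a clinician may well note one. The plan simply does not provide for it.

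**The 1.0 mm margin is not a trade for safer surgery.** A reader might infer that extra bone loss is accepted in return for a surgical advantage that is then never measured. The sample size section describes the margin only as a clinically relevant threshold and ties it to no such advantage. The stated aim is efficacy under comparable surgical conditions, and the protocol does not promise to compare surgical risk. The background's main argument is avoidance of augmentation, which this trial cannot test because every patient must have bone for 11 mm implants.

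**Nerve exposure is common to both arms.** This also stands. Injury from exposing the nerves is a safety matter for all participants and says little about implant length. Only damage related to drilling or implant depth could plausibly differ between 6 mm and 11 mm.

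**Implant loss during healing may be covered by implant survival.** Possibly. Survival means still being in function at follow-up, with no start point given, so this is unclear. It would not cover nerve, bleeding, infection or wound events in any case.

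**The numbers are too small.** True for testing, as the working shows. It is not a reason to leave harms unrecorded.

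**Conclusion.** The point holds as an omission of safety data. Surgical and healing-phase harms are not defined as outcomes in either arm, no visit is assigned to record them, and no reporting of them is planned. It is neither an internal contradiction nor a flaw in the primary comparison: no estimate, test or sample size is affected.

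The gain from correcting it is limited but real. The trial could report counts by arm with honest intervals, for example an upper limit of 21.8% if none of 15 patients is affected. It could not show or refute a difference between implant lengths unless that difference were very large.

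The conclusion rests on the protocol as published. It assumes that no separate adverse-event procedure exists outside it; if one does, the protocol should refer to it. Recruitment status is not stated, and the value of the change falls as more patients have already been operated on.

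**What to change.** In Primary and secondary outcomes, add surgical and healing-phase complications to outcome (iii): altered lip or chin sensation, haemorrhage, infection, wound dehiscence, and perforation or fracture of the mandible. Define each briefly.

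- **Population and clock:** all randomised patients, counted from first surgery, so that the interval before the final restoration is covered.
- **Recording:** at surgery, at suture removal and at the existing 4-, 8- and 12-week visits. For altered sensation, record a preoperative status where still obtainable, so that a new deficit can be told from an old one, and note at each later visit whether it persists. State how sensation is checked and by whom.
- **Analysis:** in the statistical analysis plan section, report by arm the number of patients affected with exact 95% intervals, descriptively and with no claim of a powered comparison.

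**Cost:** a short amendment, one case-report-form page, a brief sensory check at visits already scheduled, and one more descriptive outcome. No change to sample size, primary analysis or treatment. For patients already operated on, data would have to come from surgical notes at three centres. These will be less complete and not standardised, and the report should state that as a limitation.

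### The 80% power at 13 per group comes from a known-SD normal formula and is not established for the planned one-sided Mann-Whitney test, whose text does not include the 1.0 mm margin

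*Combined protocol and SAP*

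**What the plan says.** The *Sample size calculation* section of the combined protocol and SAP states that "group sample sizes of 13 per group achieved 80% power to detect noninferiority using a two-sample, one-sided test". It gives the inputs as follows:

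- Margin: "The margin of non-inferiority (δ), that is the threshold value judged as clinically relevant, was 1.0 mm".
- Assumed effect: "The true difference between the means was assumed to be 0.0".
- Spread: "The data were drawn from populations with standard deviations of 0.9 and 0.9".
- Alpha: 0.025, one-sided.

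It does not say whether the calculation was for a z-test, a t-test or a rank test. On recruitment it adds: "Fifteen patients per group will be recruited to compensate for possible drop-outs".

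The *Statistical analysis plan* section says that "the one-sided Mann-Whitney U-test for MBLc values will be applied, because of the nature of the data", and then: "For primary outcome, statistical significance will be set at the alpha level of 0.025 using a one-sided test". It takes the patient as the unit of analysis. It does not mention the 1.0 mm margin.

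The *Specific Aims and Hypotheses* section sets out a null hypothesis of no difference between short and long implants in marginal bone level change (MBLc) up to 5 years. The *Baseline and follow-up examinations* section fixes the sign of MBLc: "negative values in case of bone loss".

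**The concern.** The power is quoted for one procedure and the primary analysis is another. The calculation is framed in means and SDs, while the analysis uses ranks. Nothing in the text allows for estimating the SD from about 26 patients, or for the rank test's behaviour in samples this small.

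The second gap is how the margin enters. A non-inferiority power has meaning only if the test is made against the margin. The analysis section states no shift, and the aims section states a no-difference null. An analyst who followed those two sections literally would run a different test from the one the sample size supports.

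What is at stake is the chance of demonstrating non-inferiority. A reader will take 80% as the power of the primary analysis once drop-out has reduced each group to 13, and will take the two extra patients per group as a true reserve over 5 years of follow-up. A power shortfall of this kind does not raise the risk of a false non-inferiority claim.

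**Working it through.** **Inputs** (all from *Sample size calculation*): margin δ = 1.0 mm, true difference 0, SD σ = 0.9 mm in each group, one-sided α = 0.025, target power 80%, 13 per group powered and 15 recruited. The test, a one-sided Mann-Whitney at 0.025, comes from *Statistical analysis plan*.

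**1. Reproducing the plan's figure.** Normal approximation with known SD:

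n = 2(1.960 + 0.842)² × 0.9² / 1.0² = 12.7, rounded up to 13.

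At 13 per group the standard error is 0.9 × √(2/13) = 0.353, so δ/SE = 2.833. Power = Φ(2.833 − 1.960) = Φ(0.873) = 80.9%. The stated figure reproduces, and the arithmetic is right for this formula.

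**2. Same inputs, SD estimated (t-test).** At 13 per group there are 24 degrees of freedom, the critical value is 2.064 and the noncentrality is 2.833. The noncentral t distribution gives 77.6%.

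**3. Same inputs, Mann-Whitney with the margin built in.** This assumes that 1.0 mm is added to every MBLc value in the short-implant group, that the data are normal with SD 0.9, and that there are no ties. Power was simulated with 200,000 trials per cell (simulation error about 0.1 percentage point). The exact test at 13 per group rejects at U ≥ 124 and has true size 0.0221.

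| Evaluable per group | Normal formula | t-test | Mann-Whitney, exact | Mann-Whitney, approximate, no continuity correction |
|---|---|---|---|---|
| 13 | 80.9% | 77.6% | 73.4% | 75.3% |
| 14 | 83.6% | 80.8% | 78.5% | 78.5% |
| 15 | 86.1% | 83.6% | 80.2% | 81.5% |

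Under normality the t-test needs 14 per group for 80% and the rank test needs 15.

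**4. The test as written, without the margin.** With true difference 0 and no shift, the rejection probability equals the size of the test. For the exact test at 13 per group this is 2.2%.

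**5. Dependence on the shape of MBLc.** Exact margin-shifted test, SD 0.9. The shapes are illustrative, because the documents give none.

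| Shape | 13 per group | 15 per group |
|---|---|---|
| Uniform | 69% | 76% |
| Normal | 73% | 80% |
| Logistic | 78% | 84% |
| Left-skewed gamma, shape 4 | 79% | 85% |
| t, 5 df | 81% | 87% |
| Laplace | 83% | 88% |
| Left-skewed gamma, shape 2 | 83% | 89% |
| Left-skewed exponential | 88% | 93% |

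**6. Dependence on the SD.** At 13 per group with normal data, the t-test reaches 80% if the SD is 0.873, and the exact rank test if it is about 0.83. At SD 0.95 they give 73% and 69%.

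**The case against.** The strongest reply is that the 80% contains no arithmetic error: a normal formula is an accepted planning tool, and the section claims no more than a two-sample one-sided test. This stands as far as it goes. That the sponsor used the known-SD formula is an inference from the match.

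A second reply is that the 73 to 75% figure assumes normality, whereas the rank test was chosen because of the nature of the data. Four of the seven other shapes tried exceed 80%. This also stands, and it is why the conclusion is that the power is not established rather than that the trial is underpowered. On the other side, each patient's value averages two sites on each of five implants, which pulls it towards normality.

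A third reply is that uncertainty in the SD outweighs a gap of 2 to 7 points. The documents do not say whether 0.9 is per implant or per patient. If it were per implant (an assumption), the SD of a five-implant mean would be 0.9 × √((1 + 4ρ)/5). That is 0.82 at within-patient correlation ρ = 0.8 and 0.70 at ρ = 0.5, with exact rank-test power of about 81% and 92% at 13 per group. The SD could equally be larger. This limits how precisely any power can be stated, but it does not make the quoted figure the power of the planned test.

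Finally, 15 per group are recruited, and the margin question is partly separate from the power arithmetic. Both points are fair. However, the two extra patients are there for drop-out, and under normality the rank test needs both to reach 80%. The margin cannot be set aside either, since no power can be attached to the named test until its place in that test is stated. The sample size section does speak of a non-inferiority test, so the intention is clear, but the analysis section does not carry it through.

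**Conclusion.** The concern holds. With the plan's inputs, 80% at 13 per group is reached by the known-SD normal formula. The figure is 77.6% for a t-test. It is about 73 to 75% for the margin-shifted Mann-Whitney test, if MBLc is normal with SD 0.9 and the 1.0 mm shift is applied, neither of which the documents state. Against the formula's 80.9%, that is 3.3 points lower for the t-test and 5.6 to 7.5 points lower for the rank test. Other shapes give about 69% to 88%, so 80% is neither demonstrated nor excluded.

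Read literally, without a shift, the test rejects in about 2.2% of trials at the assumed true difference, so the stated power cannot belong to it.

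The practical effect is modest. With 15 evaluable per group the power is about 84% (t-test) or 80 to 82% (rank test, normal data). Under normality the drop-out reserve is then fully spent for the rank test, and one patient per group remains for the t-test. The plan should be corrected, but the sample size need not change.

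**What to change.** Keep 15 per group, the margin and alpha, and make three text changes.

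1. *Sample size calculation*: state that 13 per group was obtained by a normal approximation with known SD (power 81%), once the sponsor has confirmed the formula. Add that at 13 per group power is about 78% with a t-test and about 73 to 75% with the margin-shifted one-sided Mann-Whitney test if MBLc is normal with SD 0.9 mm, and that it may be higher or lower for other distributions. Give the figures for 15 evaluable per group: about 84% and 80 to 82%.
2. *Statistical analysis plan*: state that the one-sided Mann-Whitney test at 0.025 is applied after adding 1.0 mm to each MBLc value in the short-implant group, since bone loss is negative. Give the null as short implants being worse by 1.0 mm or more, and say whether the test is exact or approximate.
3. *Specific Aims and Hypotheses*: replace the no-difference null with the same non-inferiority null.

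The cost is one reworded paragraph, one addition to the analysis section and one aligned hypothesis. No patients are added. The only downside is a less favourable stated power at 13 per group, by about 2 to 7 points from the stated 80%.
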